Aim 3: To identify biomarkers and predictors of treatment response:

Hypothesis 3.1: We hypothesize that pathological hyperconnectivity between the pre-SMA, the Orbito-Frontal Cortex (OFC) and dorsal Anterior Cingulate Cortex (dACC) will correlate with OCD symptom severity in the pre-TMS scans.

Hypothesis 3.2: We hypothesize that (a) pathological hyperconnectivity between the pre-SMA the Orbito-Frontal Cortex (OFC) and dorsal Anterior Cingulate Cortex (dACC) and (b) early reduction of this pattern after week 1 of TMS will predict positive clinical outcomes after TMS.

III. SUBJECT SELECTION

There will be two different groups of patients with OCD in this study: one will receive active stimulation and one sham stimulation (i.e. placebo). We will recruit as many patients as are needed in order to obtain 20 completers per group (i.e. 40 patients in total). We expect an early termination rate of 30%, and we will anticipate the need to recruit and consent a total of 58 patients overall.

Inclusion Criteria:

- 1) 18-65 years of age.
- 2) Proficient in English.
- 3) A diagnosis of primary OCD (as determined by SCID).
- 4) Yale-Brown Obsessive Compulsive Scale total score ≥ 16 .
- 5) Normal (or corrected) vision.
- 6) Stable OCD medication regimen or OCD medication free for \geq 12 weeks prior to study.

7) Able to give informed consent.

Exclusion Criteria:

- 1) Current or history of neurologic or psychiatric disease (e.g., mental retardation, dementia, brain damage, or other cognitive impairment) that would interfere with ability to engage in TMS
- 2) Psychopathology not appropriate for the treatment (e.g., manic episode or psychosis)
- 3) Substance abuse or dependence that is current or within the last six months or use of an illicit drug that is not prescribed, as indicated by a urine drug screen and/or clinical inference.
- 4) Use of anticonvulsants within 2 weeks prior to study (to be ruled out by a urine drug screen.
- 5) Use of Tricyclic Antidepressants (e.g. Clomipramine).
- 6) Use of psychotropic medication is allowed (except for the limitations specified on use of OCD regimens, anticonvulsants, and tricyclic antidepressants).
- 7) Documented resistance to 4 or more valid pharmacological trials of 2 or more different medication classes (e.g. SSRIs and TCAs).
- 8) Previous exposure to TMS.
- 9) Major/chronic medical conditions.
- 10) History of head injury resulting in prolonged loss of consciousness and/or neurological sequelae.

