2.1 Phase 1: Randomized placebo controlled

Patients will be randomized to receive real or sham rTMS using the variable-sized permuted blocks randomization algorithm (with a maximum block size of 4), with randomization stratified by symptom severity (Y-BOCS total score ≤31 vs. >31) and age $(\le 34 \text{ vs.} > 34 \text{ years at entry})$, to ensure balance in these factors across arms in this small study. Randomizations will be conducted in SAS using procedures outlined by Efird (2011) [Efird, J. Blocked Randomization with Randomly Selected Block Sizes. Int. J. Environ. Res. Public Health., 8, 15-20]. The randomization codes generated by our statistician/data manager for each of the 4 strata will be communicated to the study coordinator at the time of randomization (i.e. at the patient's baseline visit), based on the stratum to which the patient belongs. Patients will be blinded to their treatment arm. Patients will receive 6 weeks of daily treatments Monday through Friday (not on weekends). There will be 3 MRI sessions that will take place (i) within 2 weeks prior to the first TMS session, (ii) at the end of week 1 of treatment and (iii) within 2 weeks after the last TMS session. Longitudinal clinical assessments will take place throughout the course of study at the end weeks 2, 4 and 6 of TMS, in addition to a last assessment 3 months after TMS. Physiological assessments to measure cortical excitability and

plasticity in the motor cortex using single and paired-pulse TMS will also take place the 1st day of treatment and at the end of weeks 2, 4 and 6 of TMS.

Baseline TMS Neurophys TMS Neurophys. TMS Neurophys TMS Neurophys. 8 & 8 8 Clinical Clinical Clinical Clinical Clinical Assessment Assessment Assessment Assessment Assessment 3 mo MRI MRI MRI TMS (6 weeks) Post-TMS

Figure 1: Clinical Trial Design for Phase 1

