5.1 Multi-Source Interference Task

The Multi-Source Interference Task (MSIT) is a cognitive paradigm that was designed to reliably identify the cingulo-frontal-parietal cognitive/attention network (CFP network) within individual subjects (Bush et al., 2006). Among other relevant brain regions, the pre-SMA and dorsal anterior cingulate cortex are activated in this 10-15 task when performed inside of the scanner. We will use this fMRI cognitive paradigm to identify our target of stimulation on an individual-subject basis.

Briefly, the MSIT presents a string of 3 numbers to subjects, which can be different combinations of 0,1,2,3 in which 2 numbers are the same and one is different (e.g. 100, 323, 221). Subjects are asked to identify what number is different by pressing one of 3 buttons available in the response box. Some trials will be congruent (e.g. 100) and some incongruent (010), depending on the position of the number that is different. Analyzing the brain response to these congruent and incongruent trials has been shown to robustly

identify these brain networks and regions at the individual level in healthy and patient populations (Bush et al., 2006).

5.2 Fear Conditioning:

All subjects randomized prior to February 27th, 2018 will undergo a 2-day fear conditioning protocol. The experiments will be carried out in a 3T scanner. In accordance with previously published procedures (Orr et al., 2000), prior to the initiation of the experiment, recording electrodes will be attached to the palm of the subject's non-dominant hand to measure SCR, and stimulating electrodes will be connected to two fingers of the subject's dominant hand through which the electric shock will be delivered. SCR will be measured through 9-mm (sensor diameter) Sensor Medics Ag/AgCl electrodes (safe for use in the magnet environment).

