Subjects will view two rooms presented on a monitor, both of which differ in color and content (e.g., an office and a kitchen). The conditioned stimuli (CSs) will be different cues in the room. The CS+ and the US will only be presented in one context (conditioning context; CX+). The other context will be used for extinction training (CX-). Neither CS+ presented in the context of the CX-, nor a CS- presented in either context, will ever be paired with the US. In one of the four possible CS-CX combinations, for example, the office will serve as the dangerous context, in which the subjects will receive electric currents only when the yellow light is on, whereas the kitchen will serve as the safe context, in which no electric currents will be delivered. On day 2, subjects are placed back in the magnet and will be presented with additional extinction trials to CSs in pseudorandomorder.

As of February 27th, 2018, the fear conditioning paradigm will no longer be administered to participants in this study. All fear conditioning data collected prior to February 27th will be analyzed.

VI. BIOSTATISTICAL ANALYSIS

Analysis of Aim 1: To compare change in OCD symptom severity by treatment group, we will utilize a mixed effects linear regression model with Y-BOCS total score as the outcome, a random effect for time (study week), a fixed effect for group (rTMS versus placebo stimulation), and the interaction between time and treatment group (which is the covariate of interest). We will also control for potential confounding by any covariates that are significantly imbalanced between the treatment groups.

Analysis of Aim 2.1: Specification of the analyses examining whether decreased connectivity between the pre-SMA, the Orbito-Frontal Cortex (OFC) and dorsal Anterior Cingulate Cortex (dACC) correlates with clinical improvement can be found below, in the MRI data section - Resting state Connectivity Analysis.

Analysis of Aim 2.2: Specification of the analyses examining whether TMS improves fear extinction retention from pre- to post-treatment, and whether increased functional activation of the fear extinction network (vmPFC, dACC, and hippocampus) during extinction recall can be found below, in the MRI data section - Fear Extinction.

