Two-tensor whole brain tractography will be implemented for tract analysis. This form of tractography involves a recursive process that both fits local parameters at each step and propagates the fiber in the most stable direction, allowing simultaneous tractography and model estimation. This model also uses a covariance matrix to measure confidence, which reduces false positives, and implements two eigenvalues per voxel, which improves resolution of and accounts for branching and crossing fibers. Whole-brain tractography will be used to best account for all potential tracts among the ROIs, which may be otherwise limited in solely ROI-based tractography (Yang et al., 2014).

Power for the Primary Aim

For the primary analysis comparing change in Y-BOCS total score by treatment group, with 20 patients per group and a two-sided alpha of 0.05, we will have 90% power to detect an effect size of 1.06. Due to the novelty of our approach, no comparable data exist to inform the power calculation. However, Mantovani et al. (2010) examined change in Y-BOCS total score among 18 OCD patients (completers) randomized to 4 weeks of similar rTMS or sham treatment. Based on their reported F-statistic comparing change in Y-BOCS total score after 4 weeks of treatment, their observed effect size,

expressed as Cohen's d (Thalheimer & Cook, 2002), was 1.8. Based on these results, we believe that our study will be adequately powered to detect anticipated effect sizes.

VII. RISKS AND DISCOMFORTS

Participation in this study poses minimal foreseeable risks. Patients may experience psychological discomfort when discussing psychiatric history and/or current psychiatric symptoms or side effects. Answering detailed questionnaires may also create some inconvenience for subjects. Confidentiality of all subjects will be protected per institutional and federal requirements.

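### The Aim 1 model omits both randomization strata and lets tests of baseline imbalance choose its covariates, so the primary model is not fixed in advance

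*Combined protocol and SAP*

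**What the plan says.** Section V.2.1 (Phase 1) allocates patients in permuted blocks of at most 4, "with randomization stratified by symptom severity" (Y-BOCS total ≤31 vs >31) and by age (≤34 vs >34), which makes four strata. The stated purpose is "to ensure balance in these factors across arms in this small study". After baseline, "Longitudinal clinical assessments will take place throughout the course of study at the end weeks 2, 4 and 6 of TMS", with one further assessment at 3 months.

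Section VI, Analysis of Aim 1, takes Y-BOCS total as the outcome with "a random effect for time (study week), a fixed effect for group (rTMS versus placebo stimulation), and the interaction between time and treatment group"; the interaction is the term of interest. The next sentence is the covariate rule: "We will also control for potential confounding by any covariates that are significantly imbalanced between the treatment groups". Neither stratification factor is listed. No candidate covariates, test, significance level or form of entry is given there or elsewhere. By contrast, the Aim 3 analysis in the same section names pre-treatment Y-BOCS as a covariate and states its entry and stay levels.

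Section VI, Power for the Primary Aim, uses 20 patients per group and two-sided alpha 0.05: "we will have 90% power to detect an effect size of 1.06". It mentions no covariate adjustment.

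**The concern.** Any baseline difference between randomized arms is chance, apart from faults in conduct. A rule that adds whatever tests as significant therefore makes the primary model a function of the data. Two statisticians who follow the text could choose different candidates, levels and forms of entry, and so fit different primary models to the same trial.

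The analysis also does not follow the randomization. The two factors thought important enough to stratify on are outside the model, and stratification makes them very unlikely to enter through the rule. When strata predict the outcome and the analysis ignores them, the standard error is too large for the design: the test is conservative and gives up some power. What is at stake is the credibility of the primary test as prespecified, plus a possible small loss of power.

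**Working it through.** **1. The plan's own figures.** Noncentrality = 1.06 × √(20×20/40) = 1.06 × 3.162 = 3.352 on 38 df. Two-sided power at 0.05 is 90.4%, against 90% stated. At 0.8 SD the same formula gives 69.3%. Recruitment: 40/(1 − 0.30) = 57.1, rounded up to 58, as stated in Section III. Both reproduce without covariates.

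**2. How often the rule adds something.** The plan gives no test level, so 0.05 is assumed. For k independent candidates, P(at least one flag) = 1 − 0.95^k: 23% for k = 5, 34% for 8, 40% for 10 and 60% for 18. A simulation with 8 non-prognostic candidates gave about 33%. Eighteen is an upper end: every baseline measure described in Sections IV and V except Y-BOCS and age.

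**3. Whether it can add the strata.** With blocks of at most 4, the arms differ by at most 2 within a stratum and so by at most 4 within a factor level. The most extreme table at N = 40 is 0/20 vs 4/16: chi-square = 40 × (0×16 − 20×4)² / (20×20×4×36) = 4.44, p = 0.035 (Fisher 0.11). If the smaller level holds at least 8 patients, the lowest possible p is 0.11 (N = 40) or 0.13 (N = 58). Simulated flags, 8 settings of 40,000 trials (assumed Y-BOCS mean 25–30, SD 4–5): binary severity 10 in 320,000, binary age 0, continuous Y-BOCS 0.2–3.9%, continuous age 0.03–0.07%. With 58 randomized and 30% random dropout, either binary factor was flagged in 0.2–0.3% of trials.

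**4. Form of entry.**
- *Main effect, complete visits.* A baseline main effect acts between patients, whereas time-by-group is estimated from within-patient slopes. In 170 simulated REML fits with strata explaining 20% of slope variance, adding them as main effects moved the estimate by less than 1e-13. Mean SE was 0.264 unadjusted, 0.263 with main effects and 0.237 with time interactions (some fits gave convergence warnings).
- *Main effect, dropout* (N 58, 10% lost before each of weeks 2, 4 and 6). The p<0.05 verdict changed in 0.00% of trials with 5 or 10 candidates and 0.07–0.13% with 18.
- *By time, independent candidates explaining 0–20% of slope variance together.* The verdict differs from no adjustment in these shares of all trials:

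| Candidates | 1.06 SD | 0.8 SD |
|---|---|---|
| 5 | 1.7–2.3% | 2.8–3.9% |
| 10 | 3.1–3.8% | 5.5–6.9% |
| 18 | 5.9–6.1% | 9.2–10.6% |

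Type I error in these by-time runs was 4.4–5.0%.

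**5. Omitting the strata.** If balanced strata explain a share R² of slope variance, the unadjusted statistic has SD of about √(1 − R²), so type I error ≈ 2 × [1 − Φ(1.96/√(1 − R²))]. At R² = 0.10 this is 2 × [1 − Φ(2.066)] = 3.9%. Simulation (N 40, 100,000 trials per cell, severity stratum prevalence 10–40%):

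| R² | Type I, unadjusted | Power at 0.8 SD, unadjusted vs adjusted | Power at 1.06 SD, unadjusted vs adjusted |
|---|---|---|---|
| 0 | 5.0–5.1% | 69 vs 69% | 90 vs 90% |
| 10% | 4.0–4.1% | 70 vs 73% | 91 vs 93% |

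Adjusted type I error was 4.9–5.1%.

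**6. A plausible R².** The documents give none. When the severity stratum is cut from a simulated week-0 score (mean 26–30, intercept SD 3–4, slope SD 0.7–1.0, residual SD 2–3), 12 settings gave 0–13.5% explained and a power change at 0.8 SD of −0.3 to +4.6 points. Separate runs with age non-prognostic gave −0.7 to +2.3 points in one set and about 0 to +4 in another at 0.8 SD, and −0.2 to +1.0 and about 0 to +2.5 at 1.06 SD. Unadjusted type I error was 3.8–5.4%.

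**The case against.** The strongest reply is that little changes in practice. Controlling for confounding ordinarily means a main effect, and step 4 shows that this leaves the primary result almost untouched, even with dropout. The by-time figures rest on independent candidates, but the scales in Section V.1 overlap: three measure depression and three anxiety. With an assumed common correlation of 0.5 (N 58 with dropout, about 0.85 SD), the by-time verdict change fell from 3.7% to 2.1% with 10 candidates and from 6.5% to 3.3% with 18; with 5 there was no clear difference. The count of 18 also includes the covid-19 scale, which patients randomized before February 2018 cannot have at baseline. That balanced factors go unflagged is what stratification is meant to achieve, not a fault. Finally, the severity stratum is a cut of baseline Y-BOCS, which the model already partly uses if week 0 is an outcome row.

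All of this stands as a limit on size. It does not repair the text. The plan does not state main-effect entry, does not say that week 0 is an outcome row, and leaves age out altogether. The rule stays data-dependent however small its typical effect.

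**Conclusion.** The point holds as one of prespecification and consistency with the design. It should be corrected, but it does not undermine the trial. The power gain from adjusting by time is roughly 0 to 5 points at 0.8 SD and 0 to 2.5 at 1.06 SD, assuming that the severity stratum is derived from week-0 Y-BOCS, slopes are linear and age is unrelated to change. It would be larger only if age also predicts change, for which the documents give no evidence.

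A reader might infer four stronger things that the documents do not support:
- *That omitting the strata inflates type I error.* It makes the test conservative if they are prognostic and has no effect if they are not.
- *That the 90% power claim is wrong.* It reproduces.
- *That the rule would change the verdict in up to about 10% of trials.* This needs by-time entry, as many as 18 independent candidates and a true effect of 0.8 SD; the plan states none of these.
- *That adjustment would bring a large power gain.* Strata assumed to explain 20% or 30% of slope variance give 71 vs 78–79% and 71–72 vs 83% at 0.8 SD, but those strengths exceed the 0–13.5% found when the stratum is derived from week 0.

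**What to change.** Delete the sentence on significantly imbalanced covariates. Prespecify one Aim 1 model:
- outcome: Y-BOCS at weeks 0, 2, 4 and 6;
- time in one stated form (linear, to match the single time-by-group test), group, and time-by-group as the primary test;
- severity stratum and age stratum as randomized, each with its interaction with time, since main effects alone barely move the primary estimate;
- the random-effects structure written out.

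Any other covariate adjustment becomes a named sensitivity analysis with its covariates and form of entry listed.

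This needs a documented amendment to the analysis plan, finalised before unblinding. Timing matters: Section V.5.2 ("All subjects randomized prior to February 27th, 2018 will undergo a 2-day fear conditioning protocol") shows that the trial was randomizing by early 2018, and this version is dated August 2020. No new data are needed. The statistical cost is a few degrees of freedom: with non-prognostic strata and complete visits, simulated power fell by 0.3–0.7 points at 0.8 SD and 0.2–0.4 points at 1.06 SD. With 58 randomized and 30% lost, the rounded figures at 0.8 SD were 78% without adjustment and 77% with it.

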Nevertheless, the literature on TMS for OCD remains noisy and the clinical outcomes, while promising, need improvement. An important source for this variability is the lack of individualized methods to identify and target the appropriate cortical nodes for stimulation. Our study will address this by using individual fMRI maps to identify the target and neuronavigation technology to precisely and consistently inhibit it with TMS. Another critical variable driving these inconsistencies in the field is the lack of mechanistic understanding of the effects of TMS in OCD. A priori hypotheses about disease mechanisms have driven the choices of targets of stimulations in the published clinical trials (based on a fairly robust understanding of the circuitry involved in the pathophysiology of OCD), but most studies limited themselves to measuring clinical outcomes. While this pragmatic approach is valuable, it leaves too many open questions and requires too many assumptions. Our study will innovate by proposing a translational systems neuroscience approach to understanding not only the safety and efficacy of TMS in patients with OCD, but also the physiological and anatomical changes driving (or resisting) response and remission.

II. Specific Aims

In this proposal we will apply functional neuroimaging-guided inhibitory rTMS to the pre-SMA in patients with OCD, integrating neuroimaging, behavioral and clinical research tools in a randomized controlled clinical trial. We will assess the safety and efficacy of this novel individualized strategy, study the mechanism of action at the circuit-level, and identify biomarkers and predictors of response.

Aim 1: To assess the efficacy of fMRI-guided 1HZ rTMS over the pre-SMA:

We hypothesize that patients randomized to 6 weeks of daily 1Hz rTMS will have a greater reduction in OCD symptom severity than patients randomized to identical placebo stimulation.

Aim 2: To identify the mechanisms of action of TMS at the circuit-level:

Hypothesis 2.1: We hypothesize that decreased connectivity between the pre-SMA, the Orbito-Frontal Cortex (OFC) and dorsal Anterior Cingulate Cortex (dACC) will correlate with clinical improvement.

Hypothesis 2.2: We hypothesize that TMS would improve fear extinction retention from pre- to post-treatment, and increase functional activation of the fear extinction network during extinction recall. The extinction network includes the ventromedial prefrontal cortex (vmPFC), dACC, and hippocampus.

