Analysis of Aim 3: To identify biomarkers and predictors of treatment response, we will us linear regression analysis to examine predictors of clinical improvement. The outcome will be the post-treatment Y-BOCS score, the covariate of interest will be each ROI (examined in separate models to begin with, to avoid issues of collinearity), and we will control for the pre-treatment Y-BOCS score. Univariately significant predictors will then be entered into a multivariate linear regression model using step-wise selection (alpha=0.10 to enter, alpha=0.05 to stay).

TMS neurophysiology

Numeric values for each of our 5 physiological measures will be obtained at each of the established times (baseline, week 2, week 4, week 6). A general linear model will be used to assess the difference in longitudinal progression of these measures between the active and placebo group.

MRI data

Fear Extinction

During the extinction training on day 1, the principal contrast for the fMRI data will be CS+ vs. CS-, to establish the substrates of extinction learning. During extinction recall on day 2, the principal contrast will be CS+1 vs. CS+2. Analyses of SCR will test for group x condition interactions for OCD vs. HC with respect to CS2 vs. CS1. With respect to the fMRI data, the initial analysis will involve assessing for a main effect of condition (across both groups), by comparing CS1 vs. CS2 during extinction learning and recall. Finally, voxel-wise analyses will also be performed to identify specific loci of significant group x condition interactions (OCD, HC x CS2, CS1) within designated prefrontal search territories of interest.

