others to study the medial temporal lobe memory system (Kahn, Andrews-Hanna, Vincent, Snyder, & Buckner, 2008), the frontal parietal control system involved in executive function (Vincent et al., 2006), and the default network (Buckner & Vincent, 2007), as well as initial explorations in aging (Andrews-Hanna et al., 2007). Following standard preprocessing, several additional steps are employed to condition the fMRI data for analysis of voxel-based correlations (described in Vincent 2006). Temporal band-pass filtering will remove frequencies greater than 0.08Hz. Several sources of spurious variance along with their temporal derivatives will then removed from the data through linear regression: (i) six parameters obtained by rigid body correction of head motion, (ii) the whole-brain signal averaged over a fixed region in atlas space, and (iii) the signal from a ventricular region of interest and a region centered in the white matter. In this manner, variance unlikely to be involved in spatially specific regional correlations is removed from the data. The global (whole brain) signal may correlate with respirationinduced fMRI signal fluctuations or result from global fluctuations in neuronal activity. Removing signals correlated with ventricles and white matter is an additional means of reducing non-neuronal contributions to BOLD correlations (Fox et al., 2005). Following preparation, maps of functional connectivity are obtained by plotting the correlation strength at each voxel to the time course of a seed region. Between-region correlations are obtained by extracting the time courses for multiple regions and computing the correlation coefficient between regions pairs. ANCOVA analysis will be performed covarying for the clinical and behavioral measures.

Cortical reconstruction and volumetric analysis

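### Aim 2.1 is meant to show how TMS acts on the circuit, but no active-versus-sham comparison of connectivity change is pre-specified

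*Combined protocol and SAP*

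**What the plan says.** Section II states the aim as "Aim 2: To identify the mechanisms of action of TMS at the circuit-level". Hypothesis 2.1 beneath it reads: "We hypothesize that decreased connectivity between the pre-SMA, the Orbito-Frontal Cortex (OFC) and dorsal Anterior Cingulate Cortex (dACC) will correlate with clinical improvement". It names no treatment arm.

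Section VI, Analysis of Aim 2.1, adds no model. It says that the specification of whether decreased connectivity "correlates with clinical improvement can be found below, in the MRI data section", under Resting state Connectivity Analysis. That subsection covers filtering, nuisance regression, seed maps and how the connectivity measure is computed. It ends with its only inferential sentence: "ANCOVA analysis will be performed covarying for the clinical and behavioral measures". No outcome, grouping factor, time contrast or significance level is given.

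Elsewhere in Section VI the randomised contrast is explicit. Aim 1 takes the time-by-treatment interaction on the Y-BOCS as the term of interest. For the five TMS neurophysiology measures: "A general linear model will be used to assess the difference in longitudinal progression of these measures between the active and placebo group".

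The data for the same contrast on connectivity will exist. Section V.2.1, for the randomised phase, states: "There will be 3 MRI sessions that will take place". These are before treatment, at the end of week 1 and after the last session, with no distinction by arm.

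**The concern.** Connectivity change and clinical improvement are both measured after randomisation. Their association across patients is observational, even inside a randomised trial. Patients who respond to placebo may also show connectivity change, and that would produce the hypothesised correlation in the sham arm as well as the active arm. Randomisation protects only the comparison of active with sham, and the plan does not state that comparison for connectivity.

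What is at stake is the interpretation of Aim 2.1. A positive correlation, analysed exactly as written, could be presented as the circuit mechanism of TMS when stimulation did nothing to the circuit. A null correlation would leave open whether TMS failed to move connectivity or moved it without clinical consequence.

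**Working it through.** **The plan's own figure.** Section VI, Power for the Primary Aim, gives 20 per group, two-sided alpha 0.05 and 90% power at an effect size of 1.06 on the Y-BOCS. For a two-sample t-test, df = 2 × 20 − 2 = 38, the critical t is 2.024, and the noncentrality is d × √(n/2) = 1.06 × √10 = 3.352. Power is 0.904, so the stated 90% reproduces. The documents give no figure for Aim 2.1.

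**Set-up for the illustration.** These are assumptions, not figures from the documents:
- 20 patients per arm, arms pooled for the correlation (the plan does not say whether they are);
- connectivity change c (a fall scored as positive) is standard normal in both arms, so TMS has no effect on connectivity;
- improvement = r·c + √(1 − r²)·noise + 1.06·arm, with within-arm r from 0.3 to 0.5.

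The 1.06 is the plan's Y-BOCS effect size, here reached by a route other than the measured connections.

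**Analytic check.** The arm difference adds 1.06²/4 = 0.281 to the pooled variance of improvement, so the pooled correlation is r/√1.281 = r/1.132. With Fisher's z and n = 40, power is approximately Φ(atanh(ρ) × √37 − 1.96).

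| Within-arm r | Pooled ρ | atanh(ρ) × √37 | Approximate power |
|---|---|---|---|
| 0.3 | 0.265 | 1.652 | 38% |
| 0.4 | 0.353 | 2.247 | 61% |
| 0.5 | 0.442 | 2.886 | 82% |

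**Simulation** (20,000 trials per row; correlation counted when p < 0.05 two-sided in the hypothesised direction).

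| Within-arm r | Pooled correlation | Arm in the model | Active arm only (n = 20) | Active vs sham on connectivity change |
|---|---|---|---|---|
| 0.3 | 38% | 46% | 26% | about 5% |
| 0.4 | 62% | 73% | 43% | about 5% |
| 0.5 | 83% | 92% | 64% | about 5% |

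The last column is 5% by construction, because no arm effect was simulated. Adding arm to the correlation model, or using active patients only, does not turn the association into evidence that stimulation moved the circuit.

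**The reverse case.** Suppose TMS shifts both connectivity and the Y-BOCS by d = 1.06, with no within-arm link between them. The pooled correlation is then significant in about 28% of trials and the arm comparison in about 90%. The correlation and the arm contrast answer different questions.

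**What the arm comparison can detect at 20 per arm**, with the same t-test formula:

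| d on connectivity change | Noncentrality d × √10 | Power |
|---|---|---|
| 0.5 | 1.581 | 34% |
| 0.7 | 2.214 | 58% |
| 0.91 | 2.878 | 80% |
| 1.06 | 3.352 | 90% |

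These are for one connection at alpha 0.05. Splitting alpha over two connections lowers them.

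**The case against.** The strongest reply is the ANCOVA sentence. An ANCOVA normally has a grouping factor, the trial's randomised groups are active and sham, and an arm comparison may well have been intended. A reader might infer that the plan rules such a comparison out. The documents do not support that; they leave it unspecified. Nor do they support the opposite inference, that arm is the factor: the sentence names none, and the groups named in the Fear Extinction analysis of the same MRI data section are OCD and HC. What stands is a failure to pre-specify.

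The planned analysis does match Hypothesis 2.1 as worded. In the simulated scenario that hypothesis is true, so a reader who took 38% to 83% as a false-positive rate would be wrong. It is power to find a real association. The error would lie in attributing that association to TMS.

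A reader might also suppose that change over time alone could produce the correlation. A trend shared by all patients shifts means and creates no between-patient correlation; patients must differ in something that links connectivity change to improvement.

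Finally, the aim is not the primary one, and the plan does compare arms over time on five neurophysiology measures. Those are motor-cortex measures and do not stand in for pre-SMA connectivity with OFC and dACC.

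**Conclusion.** The point holds as a gap in pre-specification that affects what Aim 2.1 can conclude. As written, the plan commits to a connectivity-improvement correlation and to an ANCOVA without outcome, arm or time contrast. It does not commit to the randomised comparison that could tie circuit change to stimulation.

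The illustrative size is a significant correlation in about 38% to 83% of trials against about 5% for an arm comparison. It rests on pooled arms, an assumed within-arm correlation of 0.3 to 0.5, no TMS effect on connectivity and a Y-BOCS effect of 1.06. If the correlation were run in the active arm only, the range would be about 26% to 64%. The logical point depends on none of these values.

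A reader might go further and infer that a mechanism must be rejected if the arm comparison is not significant. The sample size does not support that: with 34% power at d = 0.5, a null comparison would be inconclusive.

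**What to change.** Replace the ANCOVA sentence with a mixed model for each of pre-SMA-OFC and pre-SMA-dACC connectivity, with session (before treatment, week 1, after treatment), arm, arm-by-session and a patient effect. Report the active-minus-sham difference in pre-to-post change with a confidence interval, and state how the two connections are handled for multiplicity.

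Report the association between connectivity change and improvement with arm in the model, as supporting evidence, and state that it will not be attributed to TMS on the correlation alone. If an arm comparison was always intended by the ANCOVA, this simply writes it down.

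The cost is analysis wording and two models on scans already scheduled, with no new patients or visits. The downside is limited power: 80% only at d of about 0.91, 58% at 0.7 and 34% at 0.5, before any multiplicity adjustment. The plan should therefore say in advance that a null arm comparison will be reported as inconclusive and not as evidence that TMS failed to engage the circuit.
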